7.4.2 Primary Effectiveness Endpoint

The primary effectiveness endpoint is defined as freedom from documented (symptomatic and asymptomatic) atrial arrhythmia (atrial fibrillation [AF], atrial tachycardia [AT] or atrial flutter

[AFL]) recurrence based on electrocardiographic data (≥ 30 seconds on arrhythmia monitoring device) during the effectiveness evaluation period (Day 91-Day 365). Acute procedural failure (i.e., failure to confirm entrance block in all PVs except those that are silent and/or cannot be cannulated post-procedure, use of a non-study catheter for PV isolation, or failure to have PFA delivery with the study catheter due to IRE system malfunctions) will also be considered a long-term effectiveness failure. Subjects without effectiveness failure who undergo a repeat ablation procedure during the blanking period where PVs were ablated with a commercially available catheter and generator will be considered non-assessable for long-term effectiveness of the IRE ablation system and thus will be excluded from this analysis. The primary analysis of the primary effectiveness endpoint will be performed in the PP analysis set.

The primary effectiveness endpoint will be assessed by testing the following hypothesis:

$$H_0: p_E \leq 0.50 \quad vs \quad H_A: p_E > 0.50 ,$$

Where p_E is the effectiveness success rate.

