### 8.2.1 Primary Endpoints

- **Acute Safety**

The primary safety endpoint is the incidence of PAEs (within seven (7) days of the initial mapping and ablation procedure). PAEs include the following AEs:

Atrio-Esophageal Fistula*	Phrenic Nerve Paralysis (permanent)
Cardiac Tamponade/perforation	Pulmonary Vein Stenosis*
Device or procedure related death*	Stroke/CVA
Major Vascular Access Complication/Bleeding	Thromboembolism
Myocardial Infarction	Transient Ischemic Attack (TIA)
Pericarditis	

\* Device or procedure related death, pulmonary vein stenosis and atrio-esophageal fistula that occur greater than one week (7 days) post-procedure are considered and analyzed as PAEs.

A 14% performance goal is set for the primary safety endpoint

- **Long term effectiveness:**

Freedom from documented (symptomatic and asymptomatic) atrial arrhythmia (AF, AT or AFL) episodes based on electrocardiographic data ( $\geq 30$  seconds on arrhythmia monitoring device) during the effectiveness evaluation period (Day 91-Day 365). Acute procedural failure (i.e., failure to confirm entrance block, with or without touch-up, in all PVs except those that are silent and/or cannot be cannulated post-procedure) will be considered a long-term effectiveness failure.

A 50% performance goal is set for the primary long-term effectiveness endpoint

Further refer to appendix 1 for definitions on long term effectiveness terms.

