### 20.3.2 Wave II Analysis Sets

- **Modified Intent-To-Treat (mITT-Wave II) Analysis Set:** The mITT-Wave II analysis set will consist of enrolled Wave II main study phase subjects who meet eligibility criteria and have had insertion of the study catheter—Subjects in this analysis set who are discontinued due to:
  - study catheter related reasons will be considered acute effectiveness failures
  - non-study catheter related reasons (other equipment, pump, anatomy that precludes treatment with the study catheter or commercially available catheter) will be excluded from the effectiveness analysis.
- **Full Analysis set (FAS-Wave II):** The FAS-Wave II Analysis Set will consist of all enrolled Wave II main study phase subjects who have had insertion of the study catheter (with or without delivery of PFA).
- **Per Protocol (PP-Wave II) Analysis Set:** The PP-Wave II analysis set will consist of Wave II main study phase subjects who satisfy the following criteria:
  - are enrolled and without major protocol deviations that would affect the integrity of the data
  - have undergone ablation (PFA) with the study catheter
  - are treated for the study-related arrhythmia
  - did not require the use of a non-study catheter for Pulmonary Vein Isolation (PVI)
  - did not require ablations outside the PV region
- **Roll-In Analysis Set:** The Roll-In analysis set will include all subjects who are enrolled in the roll-in phase. All endpoints will be analyzed for the roll-in analysis set separately.

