5 ANALYSIS SETS

5.1 Main Phase

For the analysis of study endpoints, the analysis sets defined in the following will be used:

- **Full Analysis Set (FAS):** The FAS will consist of all enrolled subjects who have had insertion of the study catheter (with or without delivery of pulse field ablation [PFA]).
- **Modified Intent-To-Treat (mITT) Analysis Set:** The mITT analysis set will consist of enrolled subjects who have had insertion of the study catheter and meet eligibility criteria.

- **Per Protocol (PP) Analysis Set:** The PP analysis set will consist of all enrolled subjects who satisfy the following criteria:
 - Have undergone ablation with the IRE ablation system.
 - Are treated for the study-related arrhythmia.
 - Are without major protocol deviations that would affect the scientific integrity of the primary safety and effectiveness data, including but not limited to the following:
 - Subjects found not meeting eligibility criteria
 - Use of the IRE ablation modality to ablate outside the PV region
 - Failure to check for entrance block for each targeted PV after adenosine/isoproterenol challenge

Eligible subjects treated with commercially available catheters for non-PV triggers that may arise during the index procedure or during repeat procedures occurring during the blanking period will be followed for the full duration of follow-up and will be evaluable for all endpoints in order to preclude potential bias that would arise from exclusion of these subject profiles from endpoint estimates.

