7.2 Subject Disposition

Disposition and accountability of the study subjects will be summarized descriptively for the following subject categories:

- **Enrolled Subjects:** Patients who sign the informed consent form (ICF).
- **Excluded Subjects:** Subjects who are enrolled but never undergo insertion of the study catheter. Excluded subjects will be subjected to safety event reporting between ICF signature and date of exclusion. Subjects who signed the ICF but are found to be ineligible prior to insertion of the catheter are also considered as excluded.
- **Discontinued Subjects:** Subjects in whom the catheter is inserted but do not undergo ablation (i.e., no energy is delivered with the study catheter).
 - Discontinued subjects will remain in follow-up for 3-months post catheter insertion.
 - If an SAE is reported for a discontinued subject, the subject will be followed until event resolution (with or without sequelae), stabilization, or until the event is adequately explained.
- **Lost to Follow-up Subjects:** Subjects in whom the catheter is inserted for which contact is lost after most recent visit (despite 3 documented attempts to contact the subject).
- **Withdrawn / Early Termination Subjects:** Subjects who withdraw consent for study participation or are withdrawn by the investigator, are terminated from the study prior to completion of all follow-up visits.
- **Completed Subjects:** Enrolled subjects who have not been excluded, discontinued, withdrawn, terminated early, or lost-to-follow-up from the study prior to the final study visit.

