7.4.2.2 Final Analysis of Primary Effectiveness Endpoint

If trial success is not declared at the early success interim, the final analysis for the primary effectiveness endpoint will use a beta-binomial model with a non-informative uniform prior Beta (1,1) based on complete 12-month follow-up data. At the time of the final analysis, the primary effectiveness endpoint will be considered as success if:

$$\Pr(p_E > 0.50|x, n) > 0.9775$$

where p_E is the 12-month effectiveness success rate. If the posterior probability of the effectiveness rate being greater than 50% is greater than 0.9775 then the study will be considered to have demonstrated effectiveness of the device.

To investigate the robustness of the analysis result, the following sensitivity analyses will be performed in the mITT and PP analysis sets unless otherwise noted at the time of the final effectiveness analysis:

- **Sensitivity to Analysis Set**

The primary effectiveness endpoint will be analyzed in the mITT analysis set as a sensitivity analysis.

- **Snap-Shot Binomial Analysis**

Number and percentage of subjects free from primary effectiveness failure will be presented along with one-sided 97.75% exact binomial lower confidence bounds. Subjects with missing outcomes will be excluded from this analysis. Missing outcomes of primary effectiveness endpoints is defined in Section 7.4.3.

- **Kaplan-Meier Analysis**

Kaplan-Meier estimates and plots will be used to characterize the time to first primary effectiveness event, including acute procedural failure and documented symptomatic/asymptomatic AF, AT, or AFL recurrence following the initial ablation procedure. This will provide a non-parametric estimate of the primary effectiveness endpoint. The Kaplan-Meier analysis will account for all follow-up time for all subjects in the analysis set. Subjects with incomplete follow-up who remain failure free will be censored at the time of last observation. The probability of freedom from primary effectiveness failure at each monthly timepoint post blanking will be presented along with the one-sided 97.75% lower confidence bound using Greenwood's variance.

- **Best-case Scenario**

The point estimate for freedom from primary effectiveness failure will be estimated by treating subjects with missing primary effectiveness outcomes as free from primary effectiveness events.

- **Worst-case Scenario**

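### The deciding effectiveness test runs in a per-protocol set that cannot contain one of the endpoint's own device failures, and protocol and SAP disagree on two further groups

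*SAP*

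**What the plan says.** **Endpoint and deciding set.** The Wave II SAP, 7.4.2, lists three acute procedural failures that count against the primary endpoint: entrance block not confirmed, a non-study catheter used for pulmonary vein isolation (PVI), and "failure to have PFA delivery with the study catheter due to IRE system malfunctions) will also be considered a long-term effectiveness failure". The same paragraph states: "The primary analysis of the primary effectiveness endpoint will be performed in the PP analysis set". The first PP criterion in SAP 5.1 is "Have undergone ablation with the IRE ablation system". SAP 7.2 defines discontinued subjects as those with the catheter inserted who "do not undergo ablation (i.e., no energy is delivered with the study catheter". Protocol 20.3.2 also makes delivery of PFA a condition of PP. Its rule that subjects discontinued for "study catheter related reasons will be considered acute effectiveness failures" belongs to the mITT definition. At the final analysis: "The primary effectiveness endpoint will be analyzed in the mITT analysis set as a sensitivity analysis".

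**Non-study catheter for PVI.** Protocol 20.3.2 admits to PP only subjects who "did not require the use of a non-study catheter for Pulmonary Vein Isolation (PVI". The primary endpoint in protocol 8.2.1 fails a subject for "failure to confirm entrance block, with or without touch-up, in all PVs", and 8.2.3 uses touch-up to mean ablation by a non-study catheter for PVI. The PP set in SAP 5.1 has no such exclusion, and SAP 7.4.2 scores these subjects as failures.

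**Commercial ablation for a non-PV trigger.** Under protocol 14.2.2.2, a subject found after catheter insertion to need ablation outside the PV region leaves the long-term effectiveness cohort and is followed to 3 months. Protocol 14.2.5 applies the same exclusion to non-PV repeat procedures in the blanking period, and 20.3.2 removes from PP subjects who needed ablation outside the PV region. SAP 5.1 keeps both groups under full follow-up and evaluable for every endpoint, and gives avoidance of bias as the reason.

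**The concern.** This is a single-arm test against a fixed goal of 50%. With no control arm to absorb a selection effect, removing subjects who are failures by definition raises the observed rate directly, and always in the device's favour. The no-delivery malfunction is written into the primary endpoint yet cannot influence the test of that endpoint.

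The other two groups raise a different problem. The same subject can be a retained failure under the SAP and absent under the protocol, so the primary success rate depends on which document is applied. For non-PV-trigger subjects at the index procedure, the SAP also assumes follow-up that the protocol does not schedule.

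**Working it through.** **The plan's own figures.** SAP Appendix I, Table 3.a (65% effectiveness, 7% safety, realistic enrolment) gives power of 0.9457 for effectiveness, 0.8853 for safety and 0.8395 jointly. Exact safety power over the table's sample-size mix is 0.883. A simulation of the adaptive design gives 0.952 for effectiveness when imputed dropouts count as non-events in the predictive probability, so joint power is about 0.952 × 0.883 = 0.84. That match depends on the dropout reading: other readings gave 0.97 or more, and the matching one misses at 60% (0.634 against 0.7289). The 1.68% effectiveness type I error in Table 3.b was not reproduced exactly. Readings that exclude dropouts from the final analysis gave 0.34% to 2.25%, all below 2.5%. Appendix I describes simulating time to failure and dropout only, with no acute failures or PP exclusions, so its error claim does not cover this point.

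**Inputs.** Beta(1,1) prior; success if Pr(p > 0.50) > 0.9775 (SAP 7.4.2.2). Enrolment of 180 or 330 with 15% effectiveness dropout (Appendix I, 10.2) leaves 180 × 0.85 = 153 or 330 × 0.85 ≈ 281 analysed. The malfunction share f and the non-study-catheter share s are assumptions. All figures are single-look unless stated.

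**(a) No delivery because of malfunction.** If the true rate is 50% with these subjects counted, PP shows 0.50/(1 − f). The critical count is the smallest x with Pr(p > 0.5 | Beta(1 + x, 1 + n − x)) > 0.9775: 89 of 153, or 158 of 281. The chance of passing is the exact binomial tail at the PP rate.

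| f | PP rate | n = 153 | n = 281 |
|---|---|---|---|
| 0 | 50.0% | 2.6% | 2.1% |
| 1% | 50.5% | 3.5% | 3.1% |
| 2% | 51.0% | 4.5% | 4.6% |
| 5% | 52.6% | 9.8% | 12.5% |

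If the excluded subjects also leave the denominator (n = 278, 275, 267; critical counts 156, 155, 150), the chances are 3.5%, 4.3% and 13.6%. The same sizes give 2.4%, 2.0% and 2.5% at a true 50%. A simulation of the adaptive design with dropout independent of outcome gives 2.2% at f = 0, then 3.5%, 4.9% and 12.3%.

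Now suppose PP subjects succeed at the planned 65% and f = 2%. PP gives power of 95.5% (n = 150), against 93.3% with the failures counted (n = 153, rate 0.65 × 0.98 = 0.637). From 281 subjects the pair is 99.9% (n = 275) against 99.6%. With 99 successes in 153, 19 added failures would be needed to lose the result.

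**(b) Non-study catheter for PVI.** Let the remaining subjects succeed at 65%. Under the SAP the rate is 0.65(1 − s). Under the protocol it stays at 65% with fewer subjects.

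| Starting n | s | SAP rule | Protocol PP rule |
|---|---|---|---|
| 153 | 2% | 93.3% | 95.5% (n = 150) |
| 153 | 5% | 84.0% | 95.4% (n = 145) |
| 281 | 5% | 97.5% | 99.9% (n = 267) |

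**(c) Non-PV trigger at the index procedure.** The evaluation period is Day 91 to Day 365: 365 − 91 + 1 = 275 days. The 3-month window closes at Day 104, so a subject followed only to then contributes at most 104 − 91 + 1 = 14 of them. If event-free, the subject is censored at the early-success analysis and is missing at the final analysis, which requires at least 335 days (SAP 7.4.3). For non-PV repeats in blanking, the protocol keeps the 12-month schedule, so there only the exclusion rule conflicts with the SAP.

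**The case against.** - **PP is prespecified, and the malfunctions are visible elsewhere.** The mITT analysis is planned at both the early-success and final looks, with tipping-point and worst-case versions at the final one, and acute procedural success counts malfunctions. This stands as mitigation, but none of these analyses decides success.
- **The size is conditional.** The malfunction rate is assumed, the inflated error arises at a true rate of exactly 50%, and little changes at 65%. The share is applied to analysed subjects although malfunction subjects would not drop out. Part of the reduced-denominator series is discreteness, as its own baselines show. The binomial figures price only the final test, not the early-success rule. All of this stands, and it limits the grade of the point rather than the point itself.
- **On non-study catheters, protocol 8.2.2 already calls their use an acute success failure, and the stricter SAP carries the detail.** Section 8.2.2 defines a secondary endpoint, while 8.2.1 gives its own definition of acute failure for the primary one, touch-up included. No passage gives the SAP precedence. The SAP rule does work against the device, so this mismatch would favour the device only if the protocol's rule were applied.
- **Part (c) need not bias upward.** That is correct. If event-free subjects are dropped as missing while any early failures stay, the rate falls. The group is also small, because patients known to need ablation outside the PV region are ineligible. What remains is a conflict between the documents and uncollected data, not a bias in a known direction.

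**Conclusion.** The concern holds and should be fixed. The no-delivery malfunction cannot enter the primary test under either document's PP definition. This is certain from the text and can only favour the device. An assumed share of 1% is enough to take the chance of a false pass above 2.5% when the true rate, counting these subjects, is 50%: 3.1% at n = 281 and 3.5% at n = 153. At the planned 65% it would seldom change the decision. The non-study-catheter mismatch can move power from 84.0% to 95.4% at an assumed 5% use from 153 subjects. The non-PV-trigger mismatch has no computed size, but the SAP's rule for index cases cannot be carried out on 3 months of follow-up.

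**What to change.** 1. In Wave II SAP 5.1 and 7.4.2, count every eligible subject with the catheter inserted and no PFA because of an IRE system malfunction as a failure in the primary effectiveness analysis. Either add these subjects to PP or make the already planned mITT analysis the deciding one. They fail at the procedure, so no extra follow-up is needed.
2. Align protocol 8.2.1 and the PP definition in 20.3.2 with the SAP rule that a subject needing a non-study catheter for PVI stays in the analysis as a failure.
3. Reconcile protocol 14.2.2.2, 14.2.5 and the PP criterion in 20.3.2 with SAP 5.1, so that non-PV-trigger subjects have one status and the follow-up the chosen analysis needs is actually collected.

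The cost is SAP wording, a protocol amendment and, if the SAP's rule is kept, follow-up to 12 months in a few index-procedure subjects. The reported success rate may be slightly lower.

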7.4.2.1 Early Success Interim Analysis of Primary Effectiveness Endpoint

At the time of the early success interim analysis, the primary effectiveness endpoint will be met if:

$$\Pr(p_E > 0.50 | x, n) > 0.9975$$

where p_E is the effectiveness success rate. If the posterior probability of the effectiveness success rate being greater than 50% is greater than 0.9975 then the study will be considered to have demonstrated effectiveness of the device at the early success interim analysis.

At the time of the early success interim analysis, the time-to-failure during the 9-month (39 weeks) post-blanking period will be modeled by using a piecewise exponential model. The model will consist of three distinct time intervals during the 9-month evaluation period: (0, 2], (2, 8], and (8, 39] weeks. Failure times during each time interval is assumed to be exponentially distributed with a different hazard rate in each segment. The model is:

$$f(t) = \exp(-th(t))$$

where

$$h(t) = \begin{cases} \lambda_1 & 0 < t \leq 2 \\ \lambda_2 & 2 < t \leq 8 \\ \lambda_3 & 8 < t \leq 39 \end{cases}$$

Vague Gamma prior distributions will be assumed for λ_1 , λ_2 , and λ_3 . Given hazard rates λ_1 , λ_2 , and λ_3 , the failure-free rate at 12 months (9 months post-blanking) p_E can then be estimated

by

$$p_E = \exp(-[2\lambda_1 + (8 - 2)\lambda_2 + (39 - 8)\lambda_3])$$

At the interim, the total number of primary effectiveness events and the total subject exposure time will be used to update the vague Gamma prior and obtain the posterior Gamma distribution for each segment. Then 10,000 random hazard rates will be sampled from the posterior distribution for each segment and each triplet set of hazard rates will be used to calculate p_E . The distribution of p_E is estimated based on the 10,000 calculated p_E s. If the probability of p_E being greater than 50% is greater than 0.9975 (99.75%), the trial will declare early success.

To investigate the robustness of the analysis result, the following sensitivity analyses will be performed in the mITT and PP analysis sets at the time of the early success interim analysis with the available data:

- **Sensitivity to Analysis Set**

The primary effectiveness endpoint will be analyzed in the mITT analysis set as a sensitivity analysis.

- **Kaplan-Meier Analysis**

Kaplan-Meier estimates and plots will be used to characterize the time to first primary effectiveness event, including acute procedural failure and documented symptomatic/asymptomatic AF, AT or AFL recurrence following the initial ablation procedure. This will provide a non-parametric estimate of the primary effectiveness endpoint. The Kaplan-Meier analysis will account for all follow-up time for all subjects in the analysis set. Subjects with incomplete follow-up who remain failure free will be censored at the time of last observation. The probability of freedom from primary effectiveness failure at each monthly timepoint post blanking will be presented along with the one-sided 99.75% lower confidence bound using Greenwood's variance.

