6 SAMPLE SIZE JUSTIFICATION

A Bayesian adaptive design will be utilized to select the final sample size of the trial. Two sample size selection interim analyses will be performed based on the primary effectiveness endpoint. The first sample size selection interim analysis will be performed when enrollment in the mITT analysis set reaches 180. From simulations with realistic enrollment scenario, at this first interim timing, it is expected that about 30% of subjects will have between 3- and 6-months follow-up, about 18% of subjects will have between 6- and 9-months follow-up, and about 2% of subjects will have between 9- and 12-months follow-up. Predictive probabilities for trial success for the effectiveness endpoint will be used to determine whether the sample size of 180 will be sufficient or if the trial will continue enrollment. If the predictive probability with the current sample size of 180 is greater than 90%, or if the predictive probability with the maximum sample size of 330 is less than 2.5%, then enrollment will be stopped.

In case of continuation of enrollment, the second sample size interim analysis will be performed when enrollment in the mITT analysis set reaches 255. From simulations with realistic enrollment scenario, at this second interim timing, it is expected that about 27% of subjects will have between 3- and 6-months follow-up, about 27% of subjects will have between 6- and 9-months follow-up, and about 19% of subjects will have between 9- and 12-months follow-up. Predictive probabilities for trial success for the effectiveness endpoint will be used to determine whether the sample size of 255 will be sufficient or if the trial will continue to the full sample of 330. If the predictive probability with the current sample size of 255 is greater than 90%, or if the predictive probability with the maximum sample size of 330 is less than 2.5%, then enrollment will be stopped.

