Under the assumption of 7% and 65% rates for the primary safety and effectiveness endpoints respectively, the study will be adequately powered for trial success (over 80%). The highest type I error rates were estimated in the following two scenarios: 1) the true primary safety rate was on the decision boundary (i.e., equal to 14%) and the device was assumed to be very effective, and 2) the true primary effectiveness rate was on the decision boundary (i.e., equal to 50%) and the device was assumed to be very safe. In both scenarios, the overall type I error for claiming success for both safety and effectiveness is controlled at 2.5%. For details of the simulation results of power and type I error, please refer to Appendix I - Adaptive Design Simulation Report.

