10.2 Sample Size Justification

The methods described in Broglio et al.¹ will be used to determine the sample size based on the effectiveness endpoint. Sample size selection interim analyses will be performed when 180 and 255 patients are enrolled in the mITT analysis set. Predictive probabilities for trial success will be used to determine whether the sample size at the time of the interim analysis will be sufficient or

if the trial will continue to the full sample of 330. The power for testing the primary safety endpoint is greater than 80% at all sample sizes greater than or equal to 180 subjects, assuming a primary safety rate of 7% with a performance goal of 14%.

It is assumed that there is a 5% dropout rate for the safety endpoint and a 15% dropout rate for the effectiveness endpoint. The sample size will provide greater than 80% power at one-sided significance level of 2.5% for each endpoint assuming that a true safety rate of 7% and a true effectiveness rate of 65% compared to the performance goals of 14% and 50% respectively.

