where TTE_{ij} represents the time to event for patient i in time period j . For patient i , his or her imputed exposure time for time interval j would be $EXP_{ij} + TTE_{ij}$. If the imputed exposure time is less than or equal to the end of the time interval, the patient will be considered an event, otherwise, the sampled h_j for the next time interval will be used to generate a time for the next time interval and impute the exposure time. The patient time will be censored at 39 weeks if the imputed time for the last time interval is greater than 39 weeks. Additionally, a censoring time will be sampled from an exponential distribution with a rate that results in the assumed attrition rate for the effectiveness endpoint at 1 year. If this censoring time is less than the event time for the subject, then the patient will be censored at this time and will not count as an event.

This process will be repeated 1000 times to generate 1000 imputed datasets. For each of these imputed datasets, success of the final analysis for the effectiveness endpoint will be assessed once assuming we would stop at the interim with the current sample size and another time assuming we use the maximum sample size of 330. The proportion of successful trials in each case provides the predictive probability of success for the effectiveness endpoint.

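### The 0.9975 early-success decision rests on 10,000 posterior draws, so data close to the threshold can pass or fail by random seed; the effect is small and almost free to remove

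*SAP*

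**What the plan says.** **Early success.** SAP Wave II 7.4.2.1 updates a Gamma prior for the hazard in each of three post-blanking intervals. "Then 10,000 random hazard rates will be sampled from the posterior distribution for each segment", and each triplet gives one value of the 12-month success rate p_E. If the probability that p_E exceeds 50% "is greater than 0.9975 (99.75%), the trial will declare early success". Protocol 20.4.4.2 and SAP Appendix I 10.5 describe the same calculation.

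**Sample-size looks.** Appendix I 10.3.1 obtains the predictive probability by imputing outcomes: "This process will be repeated 1000 times to generate 1000 imputed datasets". SAP section 6 stops enrollment as sufficient "If the predictive probability with the current sample size of 180 is greater than 90"%. It also stops enrollment as futile when the figure computed for 330 subjects falls below 2.5%. The same rules apply at 255.

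**Final tests.** These are beta-binomial with a Beta(1,1) prior and need no sampling. For effectiveness: "If the posterior probability of the effectiveness rate being greater than 50% is greater than 0.9775 then the study" has shown effectiveness (7.4.2.2).

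Neither document gives a random seed, a Monte Carlo error, or a rule for a result that lies within simulation error of a threshold.

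**The concern.** A threshold of 0.9975 judges a tail of 0.0025. With 10,000 draws, that is 25 draws on the wrong side of 50%, and a count near 25 varies by about 5 from run to run. Two correct runs of the same program on the same locked data could reach opposite decisions.

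The decision has consequences. The protocol summary (Statistical Analysis) ties early success to filing for CE Mark while follow-up continues. Protocol 20.4.4.3 and SAP 7.4.2.2 then make the final effectiveness analysis descriptive. Early success is also the expected route: Table 3.a of Appendix I puts it at 0.8316 for a 65% effectiveness rate and a 7% safety rate. An independent rerun of borderline data should reproduce the filed result, and under the written method it need not.

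**Working it through.** **Inputs from the SAP.** 10,000 draws and threshold 0.9975 (7.4.2.1); 1,000 imputations (10.3.1); thresholds 0.90 and 0.025 (section 6); Gamma(1,1) prior for the early-success model (10.5); hazard ratios 38.06 : 1.71 : 1 and the Table 1 enrollment rates (10.6); 5% and 15% dropout (10.2).

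**Reproducing the plan's own figures.** The documents give no Monte Carlo error for the interim decisions, so the nearest checkable figures come first.
- Table 2 at 65%: h3 = −ln(0.65) / (2×38.06 + 6×1.71 + 31) = 0.43078 / 117.38 = 0.0037, so h1 = 0.1397 and h2 = 0.0063. These match.
- Win Safety at 7%/65%: exact power with 5% random dropout is 0.8255, 0.9396 and 0.9818 at N = 180, 255 and 330. Weighted by the Table 3.a split: 0.5535×0.8255 + 0.2854×0.9396 + 0.1611×0.9818 = 0.883, against 0.8853.
- Win Effect at 65%: 0.942 (330 simulated trials, SE about 0.013) against 0.9457 when dropouts count as event-free. With dropouts excluded it is 0.974, which does not match.
- Not reproduced: the early-success share (0.67 to 0.78 against 0.8316) and the N=180 share (0.62 or 0.34 against 0.5535). The flip frequencies below are therefore approximate. The standard errors do not depend on them.

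**Monte Carlo error, SE = √(p(1−p)/M).**

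| Rule | p | M now | SE now | Larger M | SE then |
|---|---|---|---|---|---|
| Early success | 0.9975 | 10,000 | 0.0005 | 1,000,000 | 0.00005 |
| Enough subjects | 0.90 | 1,000 | 0.0095 | 10,000 | 0.003 |
| Futility | 0.025 | 1,000 | 0.0049 | 10,000 | 0.0016 |

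For early success, 0.0005 / 0.0025 = 20% of the tail.

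**Chance of passing over seeds (exact binomial).** Early success needs more than 9,975 of 10,000 draws.

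| True posterior | 0.9965 | 0.9970 | 0.9975 | 0.9980 | 0.9985 |
|---|---|---|---|---|---|
| P(pass) | 3% | 16% | 47% | 84% | 99% |

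For the 90% rule (more than 900 of 1,000), P(pass) is 14% at 0.89, 48% at 0.90 and 85% at 0.91.

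**One dataset.** Assume exposure of 272, 612 and 1,476 person-weeks in the three intervals, 30, 4 and 7 events, and Gamma(1,1). From 20 million draws the posterior probability is 0.9975. A run of 10,000 draws then passes a little under half the time (about 45%).

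**How often this arises at N=180, Gamma(1,1).** At a 65% (60%) true rate, 12% (6%) of simulated trials have a posterior between 0.9965 and 0.9985. Three separate simulations put the average wrong-decision rate at 1.8% to 2.4% (1.2% to 1.4%).

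**Flips with the sample-size rules in force.** Each Monte Carlo step was run twice on identical data, with 1,000 trials per rate and dropouts excluded.

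| Decision that differs between runs | p_E = 0.65 | 0.60 | 0.50 |
|---|---|---|---|
| Early success | 2.1% | 2.4% | 0.3% |
| Selected N or futility stop | 4.0% | 2.2% | 5.5% |
| Eventual effectiveness win | 0.1% | 0.3% | 0.3% |

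In the version that reproduces Win Effect (330 trials, 65%), early success flips in 1.8%. The eventual win rarely flips because 87% to 96% of trials in the borderline band also pass the final test at p_E of 0.60 to 0.65.

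**The case against.** A reader might infer that the draw count inflates Type I error, or that the trial's conclusion depends on the seed. The evidence supports neither.

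- **Type I error.** At a true rate of 50%, 10,000 draws move the early-success probability by only about 0.01 to 0.02 percentage points. At 65% it falls by about 0.5 points, so the noise is slightly conservative there. Appendix I 10.6 says the virtual trials followed the pre-specified interim rules. If they used the same draw counts, which is not stated, the reported 1.68% already contains this noise.
- **Final answer.** A missed early success proceeds to a final test with no Monte Carlo step, hence the 0.1% to 0.3% above. The safety test has no Monte Carlo step at either analysis.
- **Reach.** At N=180, 88% to 94% of simulated trials lie outside the borderline band.
- **Sample-size rules.** They select N or stop for futility and make no success claim.
- **Safeguards.** SAP 7.4.2.1 adds a Kaplan-Meier estimate with a one-sided 99.75% lower bound at the same look. SAP sections 3 and 8 give the interims to an independent statistician. Nothing in the documents suggests that a seed could be chosen for its result.
- **The prior matters more.** In the one-dataset example, replacing Gamma(1,1) (10.5) with Gamma(0.1, 0.1) (10.3.1) moves the posterior from 0.9975 to 0.9993, or 3 to 4 Monte Carlo standard errors. Section 7.4.2.1 says only that the prior is vague.

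All of this stands and keeps the point small. It does not remove it. The Kaplan-Meier bound is supportive and does not decide; independence does not make a run reproducible; and a chance pass at the early look meets no later formal test.

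**Conclusion.** The point holds as a minor, avoidable weakness in one confirmatory decision. The standard error of 0.0005 at the 0.9975 threshold and the near coin-toss for data at that threshold follow from the SAP's own numbers. The frequencies, 6% to 12% of trials in the band and a wrong decision in about 1% to 2.5% on average, assume N=180, a 60% to 65% true rate, the SAP hazard pattern and a Gamma(1,1) prior, and are approximate. Type I error and the eventual effectiveness win are essentially unchanged. What remains is that a borderline early-success claim may not be reproducible, and that claim would support a filing. The 1,000 imputations are a lesser matter, because they affect only enrollment or a futility stop.

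**What to change.** In SAP Wave II 7.4.2.1 and Appendix I 10.5, compute the early-success posterior without sampling. The condition p_E > 0.50 is the same as 2h1 + 6h2 + 31h3 < ln 2, and the left side is a weighted sum of three independent gammas that can be integrated numerically. This removes the seed altogether. Alternatively, use about 1,000,000 draws (SE 0.00005) with a seed fixed in the SAP.

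In Appendix I 10.3.1, raise the imputations from 1,000 to at least 10,000 and fix the seed there too. The SE falls from 0.0095 to 0.003 at the 90% rule and from 0.0049 to 0.0016 at the futility rule.

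Thresholds, look times and sample sizes stay as they are. The cost is seconds of computing and a short SAP revision before the interims. State the Gamma prior in 7.4.2.1 in the same revision, since extra precision is of little use while the prior is not named there.
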